Session Documentation Form	To record the date and length of each visit, and the length of time spent traveling to and from each visit	After each session; both PREVENT and EUC participants
Telephone Log	Record duration and purpose of all telephone calls to participant	Every phone call between CHW and participant; both PREVENT and EUC participants
Telehealth Documentation Form	To record the date, start time, and end time of each telehealth visit	After each telehealth visit
Treatment Note	Record any notes relevant to the participant's treatment	After each session

Treatment Satisfaction Form	Rate participant's level of satisfaction with the	At the end of session 6 and the last booster
	intervention, and how much they felt the intervention	session via phone calls from study staff;
	respected their cultural beliefs	both PREVENT and EUC participants

Table 5. Conceptualization of Study Measures

Primary Outcome:		
Number of diabetes-specific and other ED	- EMR review	FU ¹
visits and hospitalizations over 12 months	- Self-report	
Secondary Outcomes and Potential Mediato	rs:	•
Diabetes Self-Management	- Diabetes Self-Care Inventory-Revised (DSCI-R)	Baseline, FU
Subjective access to care	- Patient Satisfaction Questionnaire-18	Baseline, FU
Objective access to care	- DM Quality Metrics	Baseline, FU
Exploratory Outcomes:		
Glycemic Control	- Hemoglobin A1c	Baseline, FU
Depression	 Patient Health Questionnaire (PHQ-9) Columbia Suicide Severity Rating Scale (for participants who express suicidal ideation) 	Baseline, FU, Suicidal ideation suspected
Quality of Life	- Diabetes Quality of Life Brief Clinical Inventory	Baseline, FU
Diabetes Health Beliefs	- DM-Specific Health Beliefs Model Scale	Baseline, FU
Intervention Costs	 CHW interventionist time Time spend supervising the CHW interventionists Medical costs 	
Potential Treatment Modifiers		
Built Environment	Community Needs Index (CNI) Access to healthy food, neighborhood safety, transportation to medical appointments	Baseline
Health Literacy	- Literacy Assessment for Diabetes (LAD)	Baseline
Demographics	- Age, sex	Baseline
Potential Covariates		
Demographic and Background Characteristics	-Age, sex, education, duration of DM, marital status, household composition, financial status, insurance status -Literacy -Alcohol Use Disorders Identification Test (AUDIT)	Baseline
Medical Comorbidity	-Health-Related Quality of Life Comorbidity Index (HRQL-CI) -Current medications (taking more than 5 medications; opioid use) -Activities of Daily Living -Previous ED use from medical records (self-report and EMR)	Baseline, FU
Cognitive Function	- Montreal Cognitive Assessment (MOCA)	Baseline

¹ FU: Follow-up assessments to take place in participants' homes at 6 and 12 months.

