the 3 physicians, they will be asked to discuss the event and reach consensus.

We will record all ED visits and hospitalizations that occur after consent, and we will code them as occurring: (1) prior to randomization; (2) after treatment begins; or (3) after randomization but before treatment begins. ED visits/hospitalizations that occur after the Index ED Visit will be assessed as follows (if the Index ED Visit results in a hospital admission, that hospitalization will not be counted toward the primary outcome):

- 1) At the 6- and 12-month follow-up assessments, the Outcome Assessor will ask about ED visits and/or hospitalizations during the previous 6 months. For each event, data on presenting symptoms, diagnostic code(s), event date(s), facility, and length of stay will be collected. The Research Assistant will verify the details of all ED visits and hospitalizations via EMR. For ED visits/hospitalizations that occur outside of Jefferson, we will obtain clinical information from the outside facility.
- 2) At 6 and 12 months, for all participants, the Research Assistant will review medical records to detect ED visits and/or hospitalizations that participants may fail to report. Details regarding each event will be recorded.

In addition, at any time that participants inform study staff (e.g., Outcome Assessor, PREVENT or EUC CHW interventionist) that they had an ED visit or hospitalization, study staff will check medical records to obtain details of the event. Study staff will contact non-Jefferson/Einstein hospitals for events that occurred outside of Jefferson or Einstein. Procedures for processing and coding ED visits and hospitalizations are detailed in the Appendix.

Participants who are permanently placed in a nursing home during the study will be censored (i.e., they will no longer have treatment sessions, follow-up assessments, or chart reviews). This is because: (1) these participants will no longer self-manage their diabetes; and (2) events that may typically require an ED visit may be handled by nursing home staff. Participants who have a temporary nursing home stay during the study will participate in all study activities.

Table 3 indicates the diagnostic codes that will be used to designate ED and hospital visits as being diabetes-related.

Table 3. Diabetes-Related Codes

Code*	Condition	
Hyper/hypoglycemic		
250.8	diabetic hypoglycemia	
251	hypoglycemic coma	
251.1	other specific hypoglycemia	
251.2, E16.2, E 16.1	hypoglycemia nos	

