6.4. Follow up assessments

Follow-up assessments will be conducted by the assessor at months 6 and 12 in participants' homes. Biweekly, the Study Coordinator will generate a computerized list of participants who are due for their follow-up assessments within the upcoming 2-week period. Included on the list will be the date of the last assessment for each participant as well as the ideal date that the assessment should take place. The date of randomization will determine when the follow-up assessments should occur. For example, if the randomization date was 3/1/17, ideally the 6-month assessment should take place on 9/1/17. Follow-up assessments will be timed so as to take place within 7 days of the ideal assessment date. If unforeseeable events prevent the follow-up assessment from occurring on time, an Out of Window Form will be completed. We will not attempt to conduct follow-up assessments on participants who are more than 30 days past due for their follow-up assessment. If a participant misses their 6 month assessment, we will attempt to contact them when they are due for their 12 month assessment.

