6.6. Missed Assessments

If a 6 or 12 month assessment is not conducted within the allowable time window, which is 30 days on either side of the target date for the follow-up assessments, it will be designated as a missed visit. The Project Director and PI reserve the right to make exceptions to this policy (e.g., illness). If any part of an assessment is conducted within the allowable time window but the entire assessment is not completed, it will be designated as an incomplete assessment.

If a participant misses a scheduled assessment, the Outcome Assessor will contact the participant to reschedule the assessment prior to the end of the visit window. If the participant is unable to complete an assessment within the acceptable visit window, the Outcome Assessor will complete a "Missed Visit Form". All attempts and contacts will be documented.

The assessor should collect what information they can by telephone. If the assessment is conducted over the telephone, any adverse experiences, hospitalizations, or other information available are recorded on the appropriate assessment forms.

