6.9. Schedule of Study Activities

Study activities will conform to the following schedule:

Screening: At the Index ED Visit

Part 1 Baseline assessment: Within 2 weeks of the Index ED visit Part 2 Baseline assessment: Within 2 weeks of the Index ED visit

Review baseline assessment: 1 week after Part 2 of Baseline Assessment

PI confirms eligibility: 1 week after Part 2 of the Baseline Assessment is

reviewed

Randomization: 3 days after eligibility is confirmed PREVENT or EUC treatment begins: 1 to 2 weeks after randomization

6 initial PREVENT or EUC treatment sessions: To be completed 4 months from baseline

6 month follow-up assessment: 6 to 7 months after randomization

3 booster PREVENT or EUC treatment sessions: 6 to 12 months after randomization

12 month follow-up assessment: 12 months after randomization

Medical chart reviews: 6 and 12 months
Pharmacy record reviews: 6 and 12 months

7: CERTIFICATION PROCEDURES

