• This may seem redundant, but Epic may not capture out of network visits, so any self-reported visits should be entered into Baseline Part 2.

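### The follow-up interview always looks back six months, so a missed or shifted visit leaves part of the primary-outcome period unasked, and the undefined offset does not exclude that time

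*Combined protocol and SAP*

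**What the plan says.** Section 6.2 gives two scheduled sources for primary events. One is the interview: at months 6 and 12, "the Outcome Assessor will ask about ED visits and/or hospitalizations during the previous 6 months". The other is a record review for every participant at the same two times, meant to find what participants leave out. In addition, an event mentioned to any staff member at any time is looked up, and outside hospitals are contacted about events elsewhere (6.2, Appendix 6).

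The visit rules are spread over three sections:

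- Section 6.4 aims for 7 days either side of the ideal date, counted from randomization. It adds: "We will not attempt to conduct follow-up assessments on participants who are more than 30 days past due". For a missed first follow-up it says: "If a participant misses their 6 month assessment, we will attempt to contact them when they are due for their 12 month assessment".
- Section 6.6 accepts a visit within "30 days on either side of the target date for the follow-up assessments".
- Section 6.9 schedules the 6-month visit "6 to 7 months after randomization".

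No section changes the look-back in any of these cases. Section 13.1.1 (Primary Aim) puts follow-up time in the Poisson model as an offset but does not define it. Section 13.1 analyses everyone who has some follow-up data.

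**The concern.** The primary outcome is a count over 12 months, so each month in the denominator should have been searched for events in the same way. A participant who misses month 6 and is seen at month 12 is asked only about the second half of follow-up. A participant first seen at month 7, which Section 6.9 allows, is never asked about the first month.

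Record review is weakest for events outside the network. Under Appendix 12 it uses Epic for Jefferson patients and a summary from the primary care physician for the others. Appendix 10 warns that "Epic may not capture out of network visits". If such an event falls in an unasked month and no other route finds it, it is lost. If that month stays in the offset, the participant's rate is understated. The rate ratio then moves if attendance, or detection by the other routes, differs between arms.

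**Working it through.** The documents give no missed-visit rate, out-of-network share or expected event rate, so there is no stated figure to reproduce. The check has two parts.

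**1. Unasked time (from the documents' own windows).** A visit at month *v* covers the interval from max(0, *v* − 6) to *v*. Thirty days is 30/30.4375 = 0.99 month. Unasked time is whatever lies between randomization and the 12-month visit and outside both intervals.

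| 6-month visit | 12-month visit | Unasked interval (months) | Length | Share |
|---|---|---|---|---|
| on time | on time | none | 0 | 0% |
| 7 days late | on time | 0 to 0.23 | 0.23 | 1.9% |
| 30 days late | on time | 0 to 0.99 | 0.99 | 8.2% |
| 30 days early | on time | 5.01 to 6 | 0.99 | 8.2% |
| on time | 30 days late | 6 to 6.99 | 0.99 | 7.6% |
| 30 days early | 30 days late | 5.01 to 6.99 | 1.97 | 15.2% |
| missed | on time | 0 to 6 | 6.00 | 50.0% |
| missed | 30 days late | 0 to 6.99 | 6.99 | 53.8% |

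The early-visit rows rest on the two-sided window in Section 6.6; Section 6.9 allows only a late 6-month visit.

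**2. Effect on events and on the rate ratio (assumed inputs).** Let *m* be the share missing the 6-month visit, *q* the share of events out of network, and *c* the share of those found by another route. The event rate is taken as constant, and unasked months are taken to stay in the offset.

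Lost share = 0.5 × *m* × *q* × (1 − *c*).

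- Low: 0.5 × 0.10 × 0.20 = 0.01.
- High: 0.5 × 0.30 × 0.40 = 0.06.
- With *c* = 0.5 these halve, to 0.5% and 3%.
- Widening *q* to 10-50% with *c* = 0 gives 0.5% to 7.5%.

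Multiplier on the rate ratio = (1 − loss in PREVENT)/(1 − loss in EUC), with *c* = 0.

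- Equal *m* and *c* in both arms: 1, so only the two rates fall.
- PREVENT 10%, EUC 20%, *q* = 20%: 0.99/0.98 = 1.010.
- PREVENT 10%, EUC 30%, *q* = 40%: 0.98/0.94 = 1.043.
- Arms swapped: 0.98/0.99 = 0.990 and 0.94/0.98 = 0.959.

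A true ratio of 0.50, the hypothesised halving, would be seen as 0.505 to 0.521 if EUC misses more, and as 0.495 to 0.480 if PREVENT misses more.

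**The case against.** The strongest reply is that the interview is one source among several.

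- Record review runs for everyone, and Appendix 12 ties it to dates (recruitment or the last review, up to the assessment), not to a fixed six months.
- Section 6.6 tells the assessor to collect what can be had by telephone and names hospitalizations.
- Nine sessions are scheduled in each arm, and an incident-event form serves both arms.
- The warning about Epic is written for the baseline data sheet, not for the primary outcome.
- Section 6.4 aims at 7 days from target and Section 6.5 sets an 80% goal for on-time visits, so two-month gaps should be rare.
- The questionnaire itself is not in the documents; its wording may differ from Section 6.2.

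Much of this stands. A reader might infer that out-of-network events in unasked months have no route into the count. The documents do not support that. What remains is that these routes are incomplete. Outside hospitals are approached only about events already known. The telephone instruction does not extend the look-back and does not name ED visits. Reports to the community health workers depend on the participant raising the event. The limit of Epic is general, even though it is stated for baseline.

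The routes are also not quite equal by arm. Telehealth contacts and action planning after an ED visit belong to PREVENT only (Section 9.1). Equal attendance therefore does not guarantee equal detection.

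**Conclusion.** The gap in the interview is real as written: about 1 month with one visit 30 days off schedule, 2 months in the early-then-late case, and 6 to 7 months when the 6-month visit is missed. Under the assumed inputs, with nothing recovered elsewhere, 1-6% of primary events are lost.

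Two stronger readings are tempting. The first is that unasked time does count in the denominator. Section 13.1.1 does not define follow-up time, so this is an inference. What can be said is that nothing removes those months: the only stated censoring rule is permanent nursing-home placement (Section 6.2). The second is that the treatment comparison is biased. Nothing in the documents shows that attendance differs by arm, and EUC was matched in intensity partly to limit attrition (Section 9.2). With equal missed visits and equal backup detection the ratio does not move. With the unequal rates assumed above it is multiplied by about 1.01-1.04, or by 0.96-0.99 in the reverse case.

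The distortion is therefore likely to be modest. The case for changing the plan is that the hole is in the primary outcome and is cheap to close. The constant event rate is also an assumption; if events cluster soon after the index visit, a missed 6-month visit would cost more than these figures show.

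**What to change.** 1. At each follow-up, ask about ED visits and hospitalizations since the last completed study assessment, or since randomization if there was none, with the date pre-filled. Unasked time then falls to 0 in every row of the table, against 0 to 6.99 months now. This matches the date-anchored chart review in Appendix 12.
2. Request outside records for any facility the participant names in that interval. Blanket requests are not feasible without a named facility.
3. Define the offset in Section 13.1.1: count person-time only to the end of the period in which events were ascertained.
4. Add a sensitivity analysis that excludes intervals without self-report, dropping both the person-time and any events found in them so that numerator and denominator match.

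The first item is one line in the form. Its downside is a recall period of up to about 12 to 13 months for participants who missed month 6, with the poorer recall that brings. The second adds some record requests; the third and fourth cost only text and analysis time. If visits are already complete, the offset rule and the sensitivity analysis can still be applied, and should be fixed before outcomes are compared by arm.

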PREVENT will begin soon after the participant's index ED visit, when many patients remain uncertain how to manage DM or how to access follow-up care. Community Health Workers (CHWs), who are race-concordant with participants, will: 1) deliver in-home DM education to increase participants' knowledge and skills; 2) use DM-specific Behavioral Activation to improve DM self-care; and 3) facilitate telehealth visits with the participant's primary care physician (PCP) and a DM nurse educator to increase access to care. The control treatment, EUC, is usual medical care that is enhanced with DM self-care education. EUC matches PREVENT in treatment intensity (i.e., 6 in-home sessions over 4 months, and 3 booster sessions over the next 8 months) and delivery of culturally relevant DM education, but does not include DM-specific Behavioral Activation or telehealth visits. The treatment comparison will identify PREVENT's specific efficacy over and above EUC.

This RCT is significant as the population ages and becomes more racially diverse, and as ED use and costs increase. This RCT is innovative because it: 1) tests the first ED-to-community intervention designed to reduce the need for ED care in AAs with DM; 2) assesses both subjective and objective indicators of access to care; and 3) defines the specific characteristics of PREVENT that confer its cultural relevance. If successful, PREVENT will meet Healthy People 2020's twin goals of reducing the personal and societal costs of DM and achieving health equity for all Americans.

The Specific Aims of this RCT are:

Primary Specific Aim: Test the efficacy of PREVENT to reduce the number of incident DM-related ED visits and/or hospitalizations over 12 months (primary outcome) in AAs with DM. Hypothesis: PREVENT will halve the number of incident DM-related ED visits and/or hospitalizations relative to EUC over 12 months.

The Secondary Aims are to:

- 1. Test the efficacy of PREVENT to increase perceived access to care over 12 months (secondary outcome). Hypothesis: PREVENT will increase Patient Satisfaction Questionnaire-18 scores to a greater extent than EUC over 12 months.
- 2. Test the efficacy of PREVENT to increase realized access to care over 12 months (secondary outcome). Hypothesis: PREVENT will increase the number of received Diabetes Quality Metrics (e.g., hemoglobin A1c testing, urine screening) to a greater extent than EUC over 12 months.

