- 3. Test the efficacy of PREVENT to improve DM self-care over 12 months (secondary outcome). Hypothesis: PREVENT will increase Diabetes Self-Care Inventory scores to a greater extent than EUC over 12 months.
- 4. Determine if increasing subjective and/or objective indicators of access to care and/or DM self-care mediates PREVENT's reduction of DM-related ED visits and/or hospitalizations. Hypothesis: PREVENT will reduce DM-related ED visits and/or hospitalizations to the extent that it increases subjective and/or objective indicators of access to care and/or improves DM self-care.

The Exploratory Aims are to: 1) determine whether PREVENT reduces "all cause" ED visits/hospitalizations relative to EUC.; 2) determine whether Community Need Index scores, literacy, age, and/or sex moderate treatment effects; 3) determine if PREVENT improves glycemic control (i.e., lowers hemoglobin A1c levels), impacts DM-related health beliefs, reduces depression, and/or improves quality-of-life; 4) identify PREVENT's treatment features that confer its cultural relevance; and 5) estimate PREVENT's costs and net financial benefit to the healthcare system.

2: RESEARCH DESIGN SUMMARY

A. Study Purpose and Rationale: This Phase-III RCT will compare the efficacy of Community Care to Prevent Diabetes Emergencies (PREVENT) vs. Enhanced Usual Care (EUC) to reduce incident DM-related ED visits and/or hospitalizations over 12 months in 230 African Americans with diabetes (aged 40 and older), following an ED visit for a DM-related condition. Note that only 156 participants were randomized.

- B. Study Design: This study is a randomized controlled clinical trial in which the unit of randomization is the person. Participants will be randomized 1:1 to PREVENT (the experimental treatment) or EUC (the control condition).
- C. Sample: The sample will comprise 230 older persons (only 156 were randomized) who meet the following criteria:

Inclusion criteria:

- 1) African American race (self-identified)
- 2) Age ≥ 40 years
- 3) Type 1 or 2 DM
- 4) A recent ED visit

Exclusion criteria:

- 1) Diagnosis of dementia
- 2) Anti-dementia medication use
- 3) Life expectancy less than one year (in the opinion of the evaluating ED physician)
- 4) DSM-V psychiatric disorders other than anxiety or depression (as per EMR)
- 5) Intoxicated
- 6) Suicidal
- 7) In police custody or currently incarcerated

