information to score the H-RQLCI, which will serve as a treatment covariate that captures overall medical comorbidity as well as changes in health status.

Intervention Costs: As an exploratory aim, we will conduct a cost-benefit analysis based on best practices in applied health economic methods. The CHW interventionists will log their time spent preparing for, scheduling, documenting, traveling, and delivering each PREVENT or EUC session. We will capture supervision and screening costs using time-logs maintained by the Study Coordinator. Other direct costs will include ED, inpatient, outpatient, and medication costs.

Treatment Process Measures: The PREVENT CHW will document: 1) the number and duration of sessions; 2) the extent and quality of participant adherence to treatment goals; 3) participants' satisfaction with the PREVENT treatment; 4) Action Plan content (and successful and unsuccessful strategies utilized), 5) participants' satisfaction with the telehealth visits; (6) number and content of EMR contacts; 7) participants' perceptions of the cultural appropriateness of the PREVENT intervention; 8) educational topics discussed at each treatment session; and 9) the extent to which family/friends participated in each visit. The EUC CHW will document: 1) the number and duration of sessions; and 2) the extent to which family/friends participated in each visit. Table 4 depicts the forms we will use to document treatment process variables.

Study Process Measures: We will query PCPs, ED staff physicians, and ED administrative staff to inquire about study implementation, engagement, concerns (e.g., impact on work flow), and acceptability of CHW collaboration. For the CHW - PCP communication via the EMR, we will measure: 1) number of PCP responses/CHW queries; 2) timeliness of PCP responses (i.e., none, or within 1, 2, or \geq 2 days); and query type (e.g., check medication dose, administration time, or side effect). These data will be analyzed descriptively to explore the relationship between PCP communication and study outcomes.

Table 4. Treatment Process Data (all forms are only for participants randomized to PREVENT unless otherwise noted)

Form	Purpose	Timing
Action Plan Form	Record steps to achieve DSM goal	Every time a goal is made or revised
Booster Session Form	Record goal progress during booster sessions	After each booster session
Community Health Worker Encounter Form	Document content of PREVENT sessions	At every session

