9.1. PREVENT

PREVENT is a collaborative intervention of PCPs, a DM nurse educator, and CHWs that aims to reduce the need for DM-related ED visits in AAs with DM. To achieve this goal, PREVENT uses culturally tailored strategies to improve DM self-care and access to care. Within 2 weeks of discharge from the ED or hospital, a CHW will begin to deliver six 90-minute in-home treatment sessions (during the 1st four months) and three booster sessions (over the next 8 months). The CHW will: 1) deliver culturally relevant DM self-care education: 2) use DM-specific Behavioral Activation to reinforce DM self-care skills, and 3) facilitate a telehealth visit with the participant's PCP (session 2), and three telehealth visits (sessions 3 and 5, and the 8-month booster session) with a DM nurse educator (Co-I [name], DNP, CDE). At every treatment session, the CHW will complete the Community Health Worker (CHW) Encounter Form. This brief standardized form characterizes CHW treatment activities and participant DM self-care practices. The CHW will upload the Form to the EMR (Epic) for the PCP's review after sessions 1 and 6 (at 4 months). This will enable the PCP to better engage the participant during the telehealth visit (session 2) and in subsequent office visits. For participants who do not have a Jefferson PCP, the CHW will fax the form to the PCP. [name] will supervise the CHW during twice monthly meetings. The CHW will make no treatment recommendations unless previously discussed with [name].

- Session 1: The CHW will establish rapport and describe the collaboration with the PCP and DM nurse educator. She will discuss the reasons for the participant's recent ED visit, experiences with DM self-care (e.g., adherence to medications, diet, glucose monitoring), and barriers (e.g., unhealthy family diet). The CHW will then review culturally relevant educational materials to build DM knowledge and skills according to national standards. The CHW will also rehearse and record a participant's questions (e.g., "Do I skip medications when traveling?") and health beliefs (e.g., "Sometimes I think prescription medications are addictive") to build confidence to discuss these issues with the PCP. The CHW will contact the JeffConnect scheduling office to schedule the PCP telehealth visit (session 2). The CHW will also refer participants (as needed) to social services to ensure that basic needs are met (e.g., safe housing, financial counseling, food security).

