Analysis: Intervention costs will be calculated using wage rates multiplied by time in preparation, documentation, delivery, training, and supervision. Fringe benefit costs will be added to staff member costs by application of prevailing rates. Material costs will include study documentation forms and educational materials. Travel expenses to/from participant homes will be captured per visit, and will be costed using current government reimbursement rates. We will estimate direct medical costs using published reimbursement rates (e.g., Medicare) for inpatient and outpatient care. The costs of DM-related ED visits and hospitalizations will be captured at baseline and months 6 and 12 for both treatment groups. Costs for DM outpatient services will be based on Medicare reimbursement rates using relevant CPT codes. We will define net financial benefit as the difference between total costs of PREVENT vs. EUC. We will conduct sensitivity analyses to determine the robustness of this calculation. The results will reveal ways to improve the efficiency of treatment delivery and to facilitate translation to practice. The sensitivity analyses will include those variables where we anticipate "real-world" uncertainty, and will include modification of key cost variables (e.g., inpatient and outpatient medical costs, based on 25th and 75th percentiles of Medicare reimbursement.)

14: STUDY TIMELINE

The Start-Up phase will take place during the first 6 months of the trial. The following will occur during the Start-Up phase: (1) hiring and training of study staff; (2) refining and implementing procedures for study recruitment; (3) creating study data files and exporting all data collection instruments into REDCap; (4) creating the randomization schedules; (5) updating the Resource List (to provide social service referrals to participants if needed); (6) creating administrative forms and study letters (e.g., to inform participants of eligibility status); and (7) convene a meeting with the DSMB and have the DSMB review and approve relevant study materials. Recruitment will take 20 months (months 7 through 26). We will expect to conduct 15 baseline assessments per month, and randomize 11 to 12. The initial 6 treatment sessions will be administered during months 7 through 32. The 6 month follow-up (FU) assessments will take place months 13 through 48 will be devoted to data cleaning and analysis, and dissemination of study findings.

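### Read literally, the Aim 5 costing formula leaves out the wages and fringe for CHW travel and scheduling time that section 6.2 has logged in both arms

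*Combined protocol and SAP*

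**What the plan says.** Section 6.2, under Intervention Costs, sets out what CHWs record in either arm: "The CHW interventionists will log their time spent preparing for, scheduling, documenting, traveling, and delivering each PREVENT or EUC session". The table of treatment process forms in the same section gives the purpose of the Session Documentation Form, which is completed in both arms: "To record the date and length of each visit, and the length of time spent traveling to and from each visit".

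The Aim 5 analysis in section 13.1.3 then states how the time is costed: "Intervention costs will be calculated using wage rates multiplied by time in preparation, documentation, delivery, training, and supervision". Fringe benefits are added to staff costs at prevailing rates. Travel has its own sentence: "Travel expenses to/from participant homes will be captured per visit, and will be costed using current government reimbursement rates".

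Section 1 states the aim in two parts, to "estimate PREVENT's costs and net financial benefit to the healthcare system". The second part is defined in 13.1.3: "We will define net financial benefit as the difference between total costs of PREVENT vs. EUC".

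**The concern.** The list of time that is logged and the list of time that is paid for do not match, and the plan gives no reason. Two logged components, travel and scheduling, have no wage attached. PREVENT is a programme of home visits, so CHW time on the road is a labour cost that a health system would have to pay.

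Aim 5 asks for PREVENT's own cost as well as for the comparison with EUC. Cancellation between the arms can protect the comparison, but it does not protect the cost of delivering PREVENT. Section 13.1.3 says the results should point to more efficient delivery and help translation to practice, and a gross cost without travel labour would serve that purpose poorly.

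**Working it through.** The plan states no cost figure, so there is nothing to reproduce. The check compares the two lists and then illustrates the size in hours.

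**Step 1. Logged time against wage-costed time.**

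| CHW time component | Logged (6.2) | In the wage formula (13.1.3) |
|---|---|---|
| Preparing | yes | yes |
| Scheduling | yes | not listed |
| Documenting | yes | yes |
| Traveling | yes, and on the Session Documentation Form | not listed; travel appears only as a per-visit expense |
| Delivering | yes | yes |

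Five components are logged and three carry over. The formula adds training and supervision, which are separate items.

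**Step 2. Omitted hours per fully treated participant, in each arm.**

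Inputs from the documents:
- Nine sessions per arm. Section 1: "EUC matches PREVENT in treatment intensity (i.e., 6 in-home sessions over 4 months, and 3 booster sessions over the next 8 months".
- Length of the six initial sessions. Section 9.1 (PREVENT): "a CHW will begin to deliver six 90-minute in-home treatment sessions".

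Assumptions, none of them in the documents:
- Boosters last 90 minutes, and EUC sessions are as long as PREVENT sessions.
- Preparation plus documentation takes 0.25 to 1.0 h per session.
- Round-trip travel takes 0.5 to 1.5 h per session.
- Scheduling takes 5 to 20 minutes per session.

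Formulas:
- Kept hours = 9 × (1.5 + preparation and documentation)
- Omitted hours = 9 × (travel + scheduling)
- Omitted share = omitted / (kept + omitted)

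Results:
- Smallest share: kept 9 × (1.5 + 1.0) = 22.5 h; omitted 9 × (0.5 + 5/60) = 5.25 h; share 5.25 / 27.75 = 19%.
- Middle values (0.5 h, 1.0 h, 10 min): kept 18 h; omitted 10.5 h; share 10.5 / 28.5 = 37%.
- Largest share: kept 9 × (1.5 + 0.25) = 15.75 h; omitted 9 × (1.5 + 20/60) = 16.5 h; share 16.5 / 32.25 = 51%.

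These are shares of direct CHW hours. Intervention cost also contains training, supervision, materials and travel expenses, all of which 13.1.3 counts, so the share of total intervention cost is smaller.

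**Step 3. The PREVENT minus EUC difference.**

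With equal completed sessions, travel time cancels. What remains is booking time for telehealth visits, which only PREVENT has: one with the primary care physician (PCP) and three with the nurse educator (section 9.1). If all four bookings go uncosted, the net omission is 4 × 5 min = 0.33 h to 4 × 20 min = 1.33 h.

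If PREVENT participants complete d more sessions than EUC participants on average, the net omission is d × (travel + scheduling) + 4 × scheduling. With travel and scheduling both at their upper values:
- d = −2: −2 × 1.833 + 1.333 = −2.3 h
- d = +2: 2 × 1.833 + 1.333 = +5.0 h

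The sign depends on completed sessions, which the plan cannot fix in advance.

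**The case against.** The strongest reply is that the wage sentence in 13.1.3 is an abbreviated summary. Section 6.2 introduces the five-part log under Intervention Costs, and Table 5 lists CHW time as a cost measure without exclusions. Collecting travel and scheduling time for costing suggests an intention to use it. The travel-expenses item might include staff time, and scheduling might count as preparation. This stands far enough that understatement follows from a literal reading and is not certain. It does not remove the point. Section 6.2 names preparing and scheduling as separate items, and the travel sentence in 13.1.3 stands apart from the wage and fringe sentences and uses reimbursement rates. If travel expenses were meant to include time, the plan needs to say so.

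The second reply is that the aim is exploratory, EUC has the same number of sessions, and the time is logged in both arms, so the costing can be settled at analysis. All of that is right, and it limits the importance of the point. It leaves PREVENT's gross cost exposed.

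A reader might go further and infer that the omission favours PREVENT in the net benefit, because only its CHW arranges telehealth visits. The documents do not support this. Section 9.1 places the booking of the session 3 nurse visit at the end of session 2, inside delivery time that is already costed, and lists the PCP booking among the session 1 tasks. Appendix 5 says the PCP booking instruction does not apply to participants without a Jefferson PCP. Step 3 also shows that the sign can reverse. A reader might equally take the percentages in step 2 as a cost understatement, but they describe CHW hours under assumed durations. Nor is any published cost shown to be wrong, since the documents report none.

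**Conclusion.** The mismatch is real and can be checked word for word. Followed as written, 13.1.3 leaves wages and fringe for travel and scheduling time out of the gross intervention cost per participant, in both arms. The documents do not allow the size to be computed. Under the assumed durations, 5.25 to 16.5 h per fully treated participant is omitted, roughly 20% to 50% of direct CHW hours and less than that as a share of total intervention cost.

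The effect on net financial benefit is small when completed sessions are equal: at most about 0.3 to 1.3 h per participant under the same assumptions, and less where bookings happen inside sessions. No direction should be claimed. No primary or secondary analysis is touched.

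**What to change.** In section 13.1.3, Aim 5, state that all CHW time logged under section 6.2 (preparing, scheduling, documenting, traveling and delivering), together with training and supervision, is costed at wage plus fringe in both arms. State also that travel expenses at government reimbursement rates cover non-time costs only, so that travel time is not counted twice. If the exclusion of travel and scheduling time was deliberate, give the reason.

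The change is to wording. The plan already has the time logged in both arms, so no new data collection is needed. The downside is a slightly higher stated intervention cost.
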